6.1.2 Scheduling

For in school scheduling of preventive care our NYUCD HCP will work with the schools.

For scheduling at alternate community-based locations our clinical teams will work with the administrator at each community-based location.

Parents/guardians of children who have consented and need to be scheduled at a community-based location will be contacted via telephone by the NYUCD HCP to schedule an appointment. They will be provided with the name and address of where we will be providing alternate care and a list of dates and times for scheduling. If they are unavailable to schedule based on the dates provided, we will contact them when new dates and times become available.

6.1.3 COVID-19 Pre-Screening and Screening Procedures

The following procedures are performed

6.1.3.1 NYUCD HCP Screening

All NYUCD HCP are required to complete the COVID-19 NYU daily screener. Any NYUCD HCP who fails on the "screener pass" will automatically be referred to the NYU COVID prevention & response team and will not report to work.

6.1.3.2 Screening In-school Students and School Staff

We will follow the school's protocol for COVID-19 screening of students and school staff.

6.1.3.3 Screening of Community-based Staff

We will follow the community-based locations protocol for COVID-19 screening of their staff.

6.1.3.4 Telephone Pre-screening of Children, Parent/Guardians at the Community-based Location

- 24 hours prior to the child's appointment the NYUCD HCP will telephone the parent/guardian and ask them the following questions:
 - Have you or your child had close contact with anyone who has a confirmed or suspected COVID-19 diagnosis in the past 14 days
 - b. Have you or your child had any flu-like symptoms like fever, coughing, shortness of breath or difficulty breathing in the past 14 days?
 - c. Have you or your child had at least two of the following symptoms in the past 14 days: chills, repeated shaking with chills, muscle pain, headache, diarrhea, sore throat, new loss of taste or smell?

d. Have you or your child traveled within a state designated by New York State's Governor's office as a restricted state?

If the parent/guardian answers **yes** to any of the above questions, the child's appointment will be scheduled for a later date (10 or more days later)

6.1.4 Clinical Room Set-up

The following procedures will be performed

The clinical treatment room set up will vary based on room size and ability to provide care at a safe distance. If the clinical room is small, only 1 station will be set up to provide care to 1 child at a time. If the clinical room is large (eg: auditorium stage or large empty room), individual stations (up to 3) will be set up and spaced at a minimum of 6' apart.

The clinical work area is disinfected with an EPA registered intermediate level surface disinfectant before supplies needed for the day are removed from suitcases or backpack. Supplies needed for the day are placed on a barrier protected clean table at least 6' away from the dental chair. The table is covered with a vinyl tablecloth. The suitcase is then placed under the clean table for storage.

A barrier protected dirty table is set up at least 6' away from the barrier protected clean clinical supply table.

The dirty table is used for the disposal of used PPE, use disposable clinical supplies, and used non-disposable clinical supplies which are placed in a biohazard labeled sharps container and placed under the dirty table Clinical Room Diagram: See illustration below:

6.1.5 Waiting Area

The following procedures will be followed in-school or at a community-based location:

6.1.5.1 Waiting Area Preparation

The following procedures are performed:

- 1. On entry to the waiting area, a hand sanitation station is set up with:
 - a. Alcohol-based hand sanitizer with 60-72% alcohol
 - b. Disinfectant
 - c. Contact free thermometer
- 2. Caried*Away* HCP will set up chairs for the waiting area ensuring a 6' distance.
- 3. Any toys, reading material, or any other objects that are difficult to clean will be removed.
- 4. A designated area will be assigned to perform the quality of life questionnaire (if applicable).

6.1.5.1.1 Waiting Room Screening Procedures

- 1. Upon arrival the dental assistant will confirm that the child and individual escorting them are wearing face masks or covering. If not, they will be supplied with a mask.
- 2. The dental assistant will ask the child and escort to apply hand sanitizer.
- 3. The dental assistant will take the temperature of the child and escort with a contact free thermometer. Note: If the child or escort has a temperature of 100.4 °F or greater they will be deferred to seek primary care evaluation and the appointment will be postponed.
- 4. If the child and escort has a temperature of less than 100.4 °F the dental assistant will escort the child to the treatment area where they will seat the child in the dental chair.

If appropriate, the person escorting the child will be seated in the waiting are with their mask on until the child has completed their treatment visit.

The waiting room seats will be spaced 6' apart and disinfected with an EPA registered intermediate level surface disinfectant between seating.

6.1.6 Examination and Diagnosis

Each program will use password-protected Apple iPads with electronic dental records pre-populated with demographic information of all students with informed consent. Student lists on the Apple iPads will be used to: collect students during the care delivery days; record clinical findings and care delivered; and generate take home forms (see below). On the scheduled care days, we will provide a gentle toothbrush cleaning, oral hygiene instruction, a toothbrush and fluoridated toothpaste. We will also carry out an examination and provide preventive care.

The examination will include a soft tissue inspection and an assessment of all primary and permanent teeth to determine the presence/ absence of decay (active or arrested), missing, filled, or sealed surfaces on all teeth.

6.1.7 Prevention

Both simple and complex care regimens provide both primary and secondary caries prevention. The goal of primary prevention is to prevent or delay the initial carious lesion using: 1) fluoride varnish for smooth surfaces (simple and complex prevention); and 2) either silver diamine fluoride (simple prevention) or sealants (complex prevention) for pits and fissures. The goal of secondary prevention is to arrest caries *in situ*, and prevent disease progression. This is accomplished with silver diamine fluoride (simple prevention) or interim therapeutic restorations (complex prevention).

6.1.8 Take Home Messages and Follow-on Care

We will provide two take-home messages, one for parents, and one for school nurses. The parents' message will identify the care provided to the child, note any additional care needed.

Parents of children without a dentist or children that require an urgent referral will be provided information on local dental providers in the following ways:

6.1.8.1 Children without a Dentist

Parents/guardians of children without a dentist can access the Caried*Away* Website Dentist finder map and link (https://dental.nyu.edu/faculty/epidemiology-health-promotion/pcori-grant.html). They are instructed to click on the map, type in their address and then click on the blue pins to access the name, address and phone number for that provider. All providers listed accept new patients, see children and, accept Medicaid and CHIP. Parents will also be provided with the NYU CariedAway- addition to Website Dentist Provider Map Instructions.

6.1.8.2 Children that require an urgent referral

Parents/guardians of children that require an urgent referral will receive the NYU Caried*Away* parent communication urgent referral email sent to them by the Caried*Away* clinical mangers. This email provides them with the CariedAway-addition to Website Dentist Provider Map Instructions and link (https://dental.nyu.edu/faculty/epidemiology-health-promotion/pcori-grant.html). The email also provides information for the NYU Department of Pediatric Dentistry.

The message for the nurses will be Excel spreadsheets that list the children seen, care provided and care needed, and that identify children who need immediate care. For the latter, we will follow each school's protocol.

6.2 Preventive Care

6.2.1 Simple prevention

Consists of a gentle toothbrush cleaning, oral hygiene instruction, an examination, delivery of silver diamine fluoride applied to all pits and fissures on bicuspids or molar teeth, and to all posterior, asymptomatic carious lesions. Fluoride varnish is then applied. Each child is given a small bag with a toothbrush, fluoride toothpaste, and a note indicating the results of the examination, the care provided, and a list of local dentists or community health centers for follow on care.

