6.2.2 Complex prevention

Consists of a gentle toothbrush cleaning, oral hygiene instruction, an examination, delivery of glass ionomer sealants to all pits and fissures on bicuspids or molar teeth, and to all asymptomatic carious lesions. Each child is given a small bag with a toothbrush, fluoride toothpaste, and a note indicating the results of the examination, the care provided, and a list of local dentists or community health centers for follow on care.

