Care will be provided by NYUCD licensed dentists, dental hygienists, nurses, and/or advanced level dental hygiene students supervised by licensed dental professionals to all participating students at all locations. After the child has completed treatment they will be required to put their mask back on and apply an alcohol-based hand sanitizer. The dental assistant will bring the child to the waiting room area. The child will be escorted back to the classroom by the school's parent coordinator or back home by the parent/guardian from the community-based, or NYUCD locations.

Simple prevention takes approximately 5 minutes and is aerosol free. It consists or a gentle tooth brush cleaning, oral hygiene instruction, an examination, delivery of silver diamine fluoride which takes approximately 1 minute to apply using Advantage Arrest Applicators to all pits and fissures on bicuspids or molar teeth, and to all posterior, asymptomatic carious lesions. Fluoride varnish is then applied which also takes 1 minute to apply.

Complex prevention takes approximately 20 minutes and is aerosol. It consists or a gentle toothbrush cleaning, oral hygiene instruction, an examination, delivery of glass ionomer sealants to all pits and fissures on bicuspids or molar teeth, and to all asymptomatic carious lesions. This takes about 5 minutes to provide care to ¼ of the mouth at a time. Fluoride varnish is then applied which takes approximately 1 minute.

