6.6 Compliance Assessment

This intervention trial depends on protocol compliance by clinicians, not students. We will train and calibrate clinicians during the summer before beginning each school year. To assess compliance, we will use qualitative and quantitative methods together with audit and feedback. Qualitatively, to ensure that the electronic records reflect actual implementation, we will visit each team in the fall and spring of each year for a one-day site visit. During the day, we will monitor adherence to protocol, particularly: student flow, caries diagnosis, and procedures delivered.

Quantitatively, we will use the elementary methods of statistical process control^{27,28}. We will examine four domains: 1) informed consent rates; 2) caries prevalence (e.g.: diagnosis); 3) care provision; and 4) outcomes. We will monitor these domains using electronic records and then verify with in-person site visits. We will start with national averages and standard deviations for school-based informed consent rate (35%), untreated caries prevalence of (21.5%). All children (100%) with permanent bicuspids and molars should receive either silver diamine fluoride (simple prevention) or traditional sealants (complex prevention) and fluoride varnish. All children (100%) with caries on their posterior teeth should receive either silver diamine fluoride (simple prevention).

We will create histograms, Pareto charts, and control charts, at the school, grade, and clinician level to identify common cause and special cause variation. Control limits will be adjusted yearly based on prior year data. If a clinician, school or grade exhibits variation that is out of the control range we will use this audit to work with the clinical team and school to provide feedback. We will continue this process during the school year.

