7.2 Statistical Methods

For caries arrest, we will first determine the per-patient proportion of carious lesions treated with simple versus complex prevention that stayed arrested throughout the length of the study. The percentage of arrested caries (at the child level) will be modeled using multilevel binomial regression. Our noninferiority margin, δ , is set at 10%. Our null hypothesis is that simple prevention is not inferior to the complex prevention by at least δ : π_{simple} - $\pi_{\text{complex}} \ge \delta$. Our alternative hypothesis is that π_{simple} - $\pi_{\text{complex}} < \delta$. We will use differences in effect sizes as estimated by confidence intervals to determine clinical non-inferiority of the two prevention methods. For the prevention of new caries, we will use generalized estimating equations (GEE) with a logit link (caries prevalence) and a negative binomial link (caries incidence), assuming an exchangeable correlation matrix, to evaluate longitudinal effects of comprehensive care untreated decay. We will identify the number of teeth at risk for each child during each follow-up interval and determine the number of those teeth in which new caries is observed at the examination that ends that interval. Primary teeth lost in each interval and new permanent teeth will not contribute to data for that interval. To explore non-linear trends in untreated decay between simple and complex prevention, we will use generalized additive models (GAMs) with non-parametric smoothers. Longitudinal effects of simple and complex prevention on academic outcomes, compared to untreated children, will be analyzed using propensity score-matching and multilevel modeling. First, we will estimate propensity scores for each participant at baseline, establishing the probability of treatment assignment conditional on observed covariates (e.g., prior academic performance). Propensity scores will be used to match treatment students to students not receiving treatment, considering multiple forms of matching
such as nearest neighbor and caliper. Treated students and matched comparators will then be analyzed using multilevel mixed effects linear regression (for academic achievement) and Poisson regression (for school absences).

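### The arms are described as treating different sets of carious lesions, and the primary arrest outcome is defined on lesions treated, so its denominator can depend on the arm

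*Combined protocol and SAP*

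**What the plan says.** **Lesions treated.** In the simple arm, 6.2.1 specifies "delivery of silver diamine fluoride applied to all pits and fissures on bicuspids or molar teeth, and to all posterior, asymptomatic carious lesions", and 6.3 says the same: "to all pits and fissures on bicuspids or molar teeth, and to all posterior, asymptomatic carious lesions". In the complex arm, 6.2.2 specifies "delivery of glass ionomer sealants to all pits and fissures on bicuspids or molar teeth, and to all asymptomatic carious lesions", and 6.3 again agrees: "and to all asymptomatic carious lesions. This takes about 5 minutes".

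**Other descriptions.** Sections 1.3 and 5.1 describe silver diamine fluoride on carious lesions, 5.8.3 on frank caries, and 6.1.7 as the simple arm's means of arresting caries; none of them sets a posterior limit for caries. The Study Summary is ambiguous, because its closing mention of posterior teeth may or may not cover the lesions. The benchmark in 6.6 reads "All children (100%) with caries on their posterior teeth should receive either silver diamine fluoride (simple prevention") and stops there, without naming the alternative that its wording leads one to expect.

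**Outcome.** Sections 2.1 and 3.2 make arrest a primary objective and endpoint, alongside prevention. Section 7.2 defines it as the "per-patient proportion of carious lesions treated with simple versus complex prevention that stayed arrested" over the study, modelled at child level with a 10% non-inferiority margin. It does not say which lesions count as treated.

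**Related provisions.** Section 6.1.6 has all primary and permanent teeth examined. Section 6.4 plans analyses of prevalence and incidence for all, adult and deciduous teeth, but none by anterior or posterior position. Section 7.3 specifies intention to treat for participants; it does not address lesions.

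**The concern.** Randomising schools balances the children and the lesions they have at baseline. It does not balance a subset of lesions picked out by what the assigned arm treats. If treated means given the arm's lesion-directed treatment, the simple arm contributes posterior lesions only and the complex arm contributes anterior and posterior lesions. A child with only anterior lesions would then enter the arrest analysis in the complex arm but not in the simple arm.

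The two arms' arrest proportions would then describe different lesions. If anterior and posterior lesions arrest at different rates, the comparison carries a component due to tooth position. That component could produce a false claim of non-inferiority or hide a true one, depending on which lesions arrest more often.

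The disagreement between sections adds a second route to the same problem. Under 6.5.2 each clinical team delivers only one arm's care, so if teams followed different sections, the variation in which lesions were treated would line up with treatment.

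**Working it through.** **1. The plan's own figure (7.1).** Inputs: arrest 20% in both arms, margin 10 points, alpha 5%, power 80%, intraclass correlation 0.10, 235 children per school.

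- n per group = (1.645 + 0.842)² × 2 × 0.20 × 0.80 / 0.10² = 197.8, rounded up to 198; total 396. This reproduces with alpha one-sided; one-sided 2.5% would give 252 per group.
- Design effect = 1 + (235 − 1) × 0.10 = 24.4.
- 396 × 24.4 = 9,662.4, matching the stated 9,662.

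No input depends on lesion position, so the sample size neither causes the problem nor changes with the fix.

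**2. Possible shift under the treated-lesion reading.** Two quantities are needed, and the documents give neither:

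- a = average anterior share of a child's treated lesions in the complex arm;
- d = arrest proportion of anterior lesions minus that of posterior lesions.

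If the arms are equally effective on posterior lesions, at rate p, the simple arm shows p and the complex arm shows (1 − a)p + a(p + d) = p + ad. The observed simple-minus-complex difference is therefore −ad. Assuming a = 10%, 20% or 30% and d = ±20 points, the size is 0.10 × 20 = 2, 0.20 × 20 = 4 and 0.30 × 20 = 6 points.

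**3. Consequence at the planned effective size.** Take 198 per arm, one-sided 5%, and non-inferiority meaning that simple is less than 10 points worse on arrest. Like 7.1, this treats each child as one binary outcome.

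- Power: simple 20%, complex 20% + ad, SE = √{[0.16 + pc(1 − pc)]/198} with pc = 0.20 + ad, power = Φ[(0.10 − ad)/SE − 1.645]. With no shift, SE = 0.0402 and power = 80%.
- Type I error: simple truly 10 points worse on posterior lesions (20% against 30%), complex observed at 30% + ad, with the same form of test.

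| a | Shift size | Power if anterior lesions arrest 20 points more often | Type I error if they arrest 20 points less often |
|---|---|---|---|
| 10% | 2 points | 62% | 12% |
| 20% | 4 points | 42% | 24% |
| 30% | 6 points | 24% | 42% |

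With d = ±10 points the shifts halve to 1, 2 and 3 points. Power is then 72%, 62% and 52%, and type I error 8%, 12% and 17%.

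**4. Whether another section removes the problem.** Section 6.4 has no split by position, and its tooth subsets concern prevalence and incidence, not arrest. Section 7.3 keeps children in their randomised group but does not define lesions. Neither settles the arrest denominator.

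**The case against.** The asymmetry is one reading, not an established fact. A reader might infer that the complex arm certainly treats anterior lesions and the simple arm never does. The documents do not settle this.

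- Treatment of anterior lesions in the complex arm is inferred from the absence of the word posterior. The unfinished benchmark in 6.6 may mean that a posterior limit was intended for both arms.
- Sections 1.3, 5.1, 5.8.3 and 6.1.7 could equally mean that neither arm is limited.
- Section 7.2 refers to lesions treated with simple prevention, not with silver diamine fluoride. Simple prevention is a package that includes varnish (3.1), and 5.3 puts varnish on every tooth. An anterior lesion in the simple arm might therefore count as treated, so it is not certain that a child with only anterior lesions would be left out.

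These points lower confidence in any one reading, but they do not supply a lesion definition. The denominator still depends on which section is followed.

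Three stronger inferences also fail.

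- *That the artefact could exceed the margin.* A 40-point gap with 30% anterior lesions gives 0.30 × 40 = 12 points. With posterior lesions arresting more often, that gap cannot occur at the 20% planning rate. An overall 20% would put posterior arrest at 20 + 40a = 24-32% for a = 10-30%, and anterior arrest 40 points lower, at −16% to −8%. It needs rates nearer the 80% in Table 1.
- *That counting all lesions would be biased against simple prevention.* In a pragmatic intention-to-treat comparison of packages, leaving some lesions without silver diamine fluoride would be part of the simple strategy. Any deficit there is a real effect.
- *That the primary outcomes should be cut to posterior teeth.* This could hide a true disadvantage of simple prevention. On untreated decay it would also narrow an outcome that parents and partners asked for (1.1.3).

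**Conclusion.** The concern stands as a defect of definition. The arm descriptions differ in both places where they are set out, other sections differ again, and the primary arrest outcome rests on an undefined set of treated lesions. On the most direct reading, that set depends on the arm, and randomisation does not protect the comparison.

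Size and direction cannot be determined from the documents. The 2-6 point shift rests on an assumed anterior share of 10-30% and an assumed 20-point difference by position. It could favour either arm, and on its own it stays inside the 10-point margin. It is still large enough to matter: under those assumptions power falls to between 62% and 24%, or type I error rises to between 12% and 42%. These figures show what is at stake; they do not estimate actual bias. The conclusion needs only that tooth position may affect arrest and that the lesion set may differ by arm.

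**What to change.** 1. **Reconcile the text.** The Study Summary and sections 1.3, 5.1, 5.8.3, 6.1.7, 6.2.1, 6.2.2, 6.3 and 6.6 should agree on which lesions each arm treats. Which clinical rule is right is for the sponsor to settle; this review takes no position.

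2. **Redefine the arrest set in 7.2.** Replace lesions treated with a set defined identically in both arms from the child's baseline examination and independent of treatment received: all asymptomatic active lesions at baseline, analysed by intention to treat.

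3. **Report arrest separately for posterior and anterior lesions.** The posterior result gives the like-for-like comparison, and the anterior result shows any difference in strategy.

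4. **State the interpretation in advance.** If the simple arm does not apply silver diamine fluoride to anterior lesions, any resulting deficit is part of the strategy effect, not bias.

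5. **Leave the untreated-decay analysis on all teeth.**

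The cost is small: one definition and one extra stratified analysis. Section 6.1.6 already records decay as active or arrested on all teeth. It does not list symptom status, so the team should confirm that the dental record holds it. The calculated sample size stays at 9,662. The one downside is that the all-lesion estimate may be slightly less favourable to simple prevention than a posterior-only one.
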